4.2 Secondary Endpoints

- Intracranial objective response rate (ORR) and intracranial progression free survival (PFS) per modified RECIST 1.1 criteria.
- Extracranial CBR, extracranial ORR, extracranial PFS per RECIST 1.1 criteria
- Global (intracranial +extracranial) CBR, global ORR, and global PFS per a combination of modified RECIST 1.1 criteria for intracranial lesions and RECIST 1.1 for extracranial disease.
- Overall survival (OS)

[figure not shown]
- Safety and tolerability will be measured by the incidence of AEs, serious adverse events (SAE), deaths, and laboratory abnormalities.

ORR is defined as the number of subjects who achieve a best overall response (BOR) of complete response (CR) or partial response (PR) divided by the number of treated subjects.

PFS is defined as the time between the date of first study dose and the first date of documented progression, as determined by the investigator, or death due to any cause, whichever occurs first. Subjects who die without a reported progression will be considered to have progressed on the date of their death. Subjects who did not progress or die will be censored on the date of their last evaluable tumor assessment. Subjects who did not have any on study tumor assessments and did not die will be censored on their date of randomization. Subjects who started subsequent anti-cancer therapy without a prior reported progression will be censored on the date of their last evaluable tumor assessment prior to the initiation of subsequent anti-cancer therapy.

OS is defined as the time from first dosing date to the date of death and will be estimated using the Kaplan-Meier product-limit method, with subjects censored at their last known date alive.

[REDACTED]

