Revised Protocol 01	28-Aug-2015	Incorporates Global Amendment and Administrative Letters 01 and 02.
Global Amendment 01	28-Aug-2015	
Major Amendment 01 Changes:
 
 • Subjects with melanoma metastatic to the brain with and without systemic lesions are now eligible for the study • Prior treatment allowed: BRAF and/or MEK inhibitors for advanced disease • Prior treatment allowed: patients who received ipilimumab as adjuvant therapy must have a 6 month washout before receiving dosing on this study 
[REDACTED]
 
 • Enrolled subjects may receive stereotactic radiation therapy (SRT) (single episode) for progression of up to 3 brain lesions • Brain edema or post SRT steroid treatment specified as ≤ 16 mg dexamethasone PO daily tapered in ≤ 4 weeks • Two interim analyses incorporated into the study design • Steering Committee replaces safety committee • Modified Response Evaluation Criteria in Solid Tumors (RECIST 1.1) incorporated in response algorithm for brain tumors • Immune-related Response Criteria and the Protocol-defined response criteria have been removed from the study • Subsections in Section 5.4 Efficacy Assessments that also appear in Appendix 3 are now deleted from protocol body 
[REDACTED]
 
 • Appendix 3 modified to reflect changes made for brain lesions.
Administrative Letter 02	15-Jul-2015	Modified the requirements for pre-treatment tumor tissue within the eligibility criteria. This change allows for submission of archival tumor tissue when an extracranial metastasis tissue specimen collected after the most recent prior systemic therapy is not available or cannot be obtained by biopsy.
Administrative Letter 01	13-Mar-2015	Corrects IND Number for Protocol CA209-204
Original Protocol	22-Sep-2014	Not applicable

SUMMARY OF KEY CHANGES OF REVISED PROTOCOL 03		
Section Number & Title	Description of Change	
Title Page	Update of study personnel	
Throughout the protocol	
 Intracranial and extracranial replace brain and systemic, respectively, for protocol-specific references throughout the document. 	

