Research Hypothesis: Treatment with nivolumab combined with ipilimumab followed by nivolumab monotherapy will provide clinical benefit to subjects with melanoma metastatic to the brain.

Objectives:

Study objectives will be applied for all treated subjects (Cohort A and Cohort B).

Primary, secondary, [REDACTED] endpoints and safety analyses will be reported in the treated subjects, for overall population, by cohorts (asymptomatic and symptomatic), and by subgroup (prior to study with or without SRT and on study with or without SRT).

Primary Objective: To assess intracranial clinical benefit rate (CBR, defined as complete response [CR] + partial response [PR] + stable disease [SD]) \geq 6 months in subjects with melanoma metastatic to the brain per modified RECIST 1.1 criteria.

Secondary Objectives:

- To assess the extracranial clinical benefit rate defined as CR+PR+SD \geq 6 months (per RECIST 1.1 criteria)
- To assess intracranial objective response rate (ORR), intracranial progression-free survival (PFS) per modified RECIST 1.1 criteria
- To assess extracranial ORR, extracranial PFS per RECIST 1.1 criteria
- To assess global CBR, global ORR, global PFS per a combination of modified RECIST 1.1 criteria for intracranial lesions and RECIST 1.1 for extracranial disease
- To assess overall survival (OS)
- To evaluate the intracranial-specific safety and tolerability of the combination regimen in patients with or without stereotactic radiotherapy (SRT) received prior to study entry, or on study.

[REDACTED]

[REDACTED]

[REDACTED]

[REDACTED]

[REDACTED]

[REDACTED]

[REDACTED]

[REDACTED]

[REDACTED]

Study Design: This is an open-label, multi-site, Phase 2 study of nivolumab combined with ipilimumab followed by nivolumab monotherapy for the treatment of subjects with melanoma metastatic to the brain.

Cohort A comprises subjects with histologically-confirmed malignant melanoma with asymptomatic intracranial metastases with or without measurable extracranial disease. Per Amendment 02, August 2016, the patient population was expanded to include Cohort B, which will enroll approximately 20 patients with symptomatic intracranial metastases who may be on steroids per protocol specifications. Symptomatic patients who are not on steroids are also eligible for Cohort B.

[figure not shown]

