3.3.1 Inclusion Criteria

1. Signed Written Informed Consent
 - a) Subjects must have signed and dated an IRB/IEC approved written informed consent form in accordance with regulatory and institutional guidelines. This must be obtained before the performance of any protocol-related procedures that are not part of normal subject care.
 - b) Subjects must be willing and able to comply with scheduled visits, treatment schedule, laboratory testing, and other requirements of the study.

2. Target Population

- a) Histologically confirmed malignant melanoma with measurable metastases in the brain
- b) **Cohort A:** At least 1 measurable intracranial metastasis ≥ 0.5 cm and ≤ 3 cm in longest diameter that has not been previously irradiated. No clinical requirement for local intervention (surgery, radiosurgery, corticosteroid therapy) or other systemic therapy.

Cohort B: Per Amendment 02 (August 2016) Subjects with neurologic signs and symptoms related to metastatic intracranial lesions are eligible per Amendment 02. Subjects must have at least 1 measurable intracranial metastasis ≥ 0.5 cm and ≤ 3 cm in longest diameter that has not been previously irradiated. No immediate requirement (within 3 weeks prior to first treatment) for local intervention (surgery, radiosurgery, corticosteroid therapy). Steroid use is permitted as defined in inclusion criterion 2e).

- c) Prior stereotactic radiotherapy (SRT) and prior excision of up to 3 melanoma intracranial metastases is permitted if there has been complete recovery, with no neurologic sequelae, and measurable lesions remain. Growth or change in a lesion previously irradiated will not be considered measurable. Regrowth in cavity of previously excised lesion will not be considered measurable. Any prior SRT to intracranial lesions or prior excision must have occurred ≥ 3 weeks before the start of dosing for this study.
- d) Must have tumor tissue available for biomarker analysis. Biopsy should be excisional, incisional, punch, or core needle. Fine needle aspirates or other cytology samples are not allowable.
- e) **Cohort A (asymptomatic):** Subjects must be free of neurologic signs and symptoms related to metastatic intracranial lesions and must not have required or received systemic corticosteroid therapy within 10 days prior to first treatment.

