8.4.2 Secondary Endpoint(s)

Secondary endpoints are as follows:

- Intracranial ORR and intracranial PFS per modified RECIST 1.1 criteria;
- Extracranial CBR, extracranial ORR, extracranial PFS per RECIST 1.1 criteria

- Global (intracranial + extracranial) CBR, global ORR, and global PFS per a combination of modified RECIST 1.1 criteria for intracranial lesions and RECIST 1.1 for extracranial disease
- OS
- Safety and tolerability will be measured by the incidence of AE adverse events, serious adverse events (SAE), deaths, and laboratory abnormalities.

Overall survival (OS) is defined as the time from first dosing date to the date of death, will be estimated using the Kaplan-Meier product-limit method, with subjects censored at their last known date alive.

Progression-free survival (PFS) is defined as the time between the date of first dose of study drug and the first date of documented confirmed progression, as determined by the investigator, or death due to any cause, whichever occurs first. Subjects who die without a reported progression will be considered to have progressed on the date of their death. Subjects who did not progress or die will be censored on the date of their last evaluable tumor assessment. Subjects who did not have any on study tumor assessments and did not die will be censored on the date of first dose of study drug. Subjects who started anti-cancer therapy without a prior reported progression will be censored on the date of their last evaluable tumor assessment prior to the initiation of subsequent anti-cancer therapy.

Overall response rate (ORR) is defined as the number of subjects who achieve a best overall response of complete response (CR) or partial response (PR) divided by the number of treated subjects. The best overall response is defined as the best response designation recorded between the date of first study dosing date and the date of progression, or the date of subsequent anticancer therapy (including tumor-directed radiotherapy and tumor-directed surgery), whichever occurs first.

Safety and tolerability will be measured by the incidence of adverse events, serious adverse events, deaths, and laboratory abnormalities.

[REDACTED]

[REDACTED]

[REDACTED]

[REDACTED]

[REDACTED]

[REDACTED]

[REDACTED]

[REDACTED]

[REDACTED]

[REDACTED]

[REDACTED]

[REDACTED]

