4 ENDPOINTS

4.1 Primary Endpoints

The primary endpoint is intracranial CBR. It is defined as the proportion of all treated subjects whose best overall response (BOR) is either a CR or PR or whose BOR was SD with duration of ≥ 6 months, as determined by modified RECIST 1.1 criteria for index intracranial lesions based on investigator review.

The BOR is defined as the best response designation recorded between the date of first study dosing date and the date of progression, or the date of subsequent anticancer therapy (including tumor-directed radiotherapy and tumor-directed surgery), whichever occurs first. In this study, BOR is specified for the intracranial, extracranial, and global compartments based on the (1) modified RECIST 1.1 criteria (intracranial), (2) RECIST 1.1 criteria (extracranial), (3) combination of modified RECIST 1.1 criteria and RECIST 1.1 criteria (global). Best response determination in trials where confirmation of complete or partial response is required: Complete or partial responses may be claimed only if the criteria for each are met at a subsequent time point as specified in protocol Appendix 3. There is no confirmation requirement for progressive disease (PD). The BOR for each patient as determined by the BICR is determined from a predefined set of rules specified within the Image Review Charter.

To ensure the accuracy of primary endpoints, analyses will be based on two sets of BOR: BOR as reported in the CRF and BOR with adjustment. BOR as reported in the CRF uses information entered in the CRF directly by investigators without adjustment. Results based on BOR with adjustments will serve as primary analysis. This decision was made after the interim database lock on 09 August 2020.

BOR with adjustment uses information entered in the CRF with the following adjustments:

- If BOR is NE, and the radiographic progression date is non-missing and prior to subsequent anti-cancer therapy start date, or subsequent anti-cancer therapy start date is missing, change BOR to PD.
- If BOR is SD, and the radiographic progression date is non-missing and duration of SD is less than 6 months and radiographic progression date is prior to subsequent anti-cancer therapy start date, or subsequent anti-cancer therapy start date is missing, change BOR to PD.
- If BOR is PR or CR, and there is preceding (confirmed or unconfirmed) PD and

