7.4.2.5 Dose Omissions

Dose omissions are not permitted for either nivolumab or ipilimumab.

7.4.4 *Diagnostic Procedures*

- By-subject listings of Diagnostic procedures will be provided for all treated subjects.

7.5 *Efficacy*

All summaries will be based on all treated subjects, unless otherwise specified. All summaries will be repeated by cohort and by SRT status, unless otherwise specified.

7.5.1 *Primary Efficacy Analysis*

The primary endpoint of intracranial CBR is determined by modified RECIST 1.1 criteria for index intracranial lesions based on investigator review. The intracranial CBR will be calculated for the all treated population with its corresponding two sided 90% exact CI using the Clopper-Pearson method. The two-sided 95% CI will also be calculated.

CBR based on BOR as reported on CRF will be analyzed using the same methodology as primary endpoint of intracranial CBR based on modified RECIST 1.1.

Central review of all images will be conducted by a Blinded Independent Central Review (BICR) specified in the Imaging Review Charter. In addition to the primary endpoint analysis, a sensitivity analysis using BICR-assessed intracranial CBR will also be performed, where both two-sided 90% exact CI and two-sided 95% CI will be calculated.

In addition, a sensitivity analysis will also be conducted to evaluate the impact of SRT on intracranial CBR by excluding the patients who received on-study SRT. This will be repeated by cohort only.

7.5.2 *Secondary Efficacy Analyses*

Secondary analyses include additional CBR results, Objective Response Rate (ORR), overall survival (OS) including OS within tumor response and prior occurrence of specific AEs, subject follow-up, subsequent therapy and progression free survival.

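### Extracranial ORR and CBR are divided by all treated subjects, although subjects with no extracranial lesion can enter; no pooled rate among those with extracranial disease is planned in the text supplied.

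*SAP*

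**What the plan says.** **Denominator.** SAP 4.2 divides subjects with "complete response (CR) or partial response (PR) divided by the number of treated subjects". Protocol 8.4.2 has the same rule: "a best overall response of complete response (CR) or partial response (PR) divided by the number of treated subjects". Neither makes an exception for a compartment. For CBR, SAP 4.1 takes "the proportion of all treated subjects whose best overall response (BOR) is either a CR or PR", or SD of sufficient duration. SAP 7.5 sets the default: "All summaries will be based on all treated subjects, unless otherwise specified". SAP 7.5.2.1 and 7.5.2.2 then apply the intracranial CBR approach to extracranial CBR and ORR, with Clopper-Pearson 95% intervals. The planning tables (Protocol Table 8.1-1, SAP Table 5-1) use 110 as the denominator in the extracranial row too.

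**Eligibility.** The target-population criterion in Protocol 3.3.1 is "Histologically confirmed malignant melanoma with measurable metastases in the brain", and nothing there asks for extracranial disease in either cohort. The Protocol Synopsis describes Cohort A as having "asymptomatic intracranial metastases with or without measurable extracranial disease". The entry for Global Amendment 01 in the document history agrees: "Subjects with melanoma metastatic to the brain with and without systemic lesions are now eligible for the study". That entry is cited only as support for the current text.

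**The concern.** Extracranial ORR and CBR are named secondary objectives, and readers will take them as measures of activity against extracranial tumour. A subject with no extracranial lesion at baseline has nothing there that can shrink or disappear, yet is counted in the denominator. The reported ORR therefore mixes drug effect with case mix: two series with the same activity but different shares of brain-only disease would report different rates.

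For CBR the problem is less defined. If brain-only subjects are entered as not evaluable, CBR falls. If they are entered as stable, or as free of disease and counted as benefit, CBR can rise. The supplied text gives no rule. The exact interval remains valid for the all-treated proportion; the difficulty is what that proportion describes.

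**Working it through.** **1. The plan's own figures.** For the extracranial planning row, 65/110 = 59.1%. Recomputed Clopper-Pearson limits are 50.8–67.0% (90%) and 49.3–68.4% (95%), as printed. The largest 95% interval width over all counts at n = 110 is 19.4 points, within the stated 20. The arithmetic in the documents is not in dispute.

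**2. Inputs.** N = 110 (SAP 5). Let p be the rate among subjects with any extracranial lesion, and q the share of treated subjects with no extracranial lesion, target or non-target. The documents give neither. Assume p = 60%, close to the 59.1% planning value, and q from 5% to 30%.

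**3. ORR.** Subjects without a lesion contribute no responders, so reported ORR = p(1 − q).

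**4. CBR.** Let s, between 0 and 1, be the share of no-lesion subjects coded as benefit. Reported CBR = p(1 − q) + qs.

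| q | Reported ORR | Reported CBR, s = 0 to s = 1 |
|---|---|---|
| 5% | 0.60 × 0.95 = 57% | 57% to 62% |
| 10% | 0.60 × 0.90 = 54% | 54% to 64% |
| 20% | 0.60 × 0.80 = 48% | 48% to 68% |
| 30% | 0.60 × 0.70 = 42% | 42% to 72% |

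**5. In counts, with 95% limits.**
- 5 of 110 without a lesion: 63/105 = 60.0% (50.0–69.4) is reported as 63/110 = 57.3% (47.5–66.7).
- 22 of 110 without a lesion: 53/88 = 60.2% (49.2–70.5) is reported as 53/110 = 48.2%. The upper limit for 53/110 in the plan's own table is 57.9%, below the 60.2% seen among those with disease.

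**6. Against the plan's benchmark.** Both planning tables take 50% as the clinically meaningful extracranial CBR and illustrate it with 65/110. If 22 subjects have no lesion and are coded as no benefit, reaching 65 requires 65/88 = 73.9% among those with disease.

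**7. Do other planned outputs already give the missing rate?**
- *Extracranial response evaluable set (SAP 6.3).* No ORR or CBR analysis in the supplied text uses it. It also requires a valid post-baseline target-lesion assessment, so it drops subjects who died or left before a scan and those with non-target disease only.
- *Forest plots by number of target lesions: 0, 1–2, ≥3 (SAP 7.5.2.2).* The compartment is not stated. A zero row makes sense mainly for an extracranial count, because every subject has a brain lesion. On that reading the row still mixes subjects with no extracranial disease and subjects with non-target lesions only.
- *Tabulated and listed BOR with reasons for not evaluable (SAP 7.5.2.2).* Useful context, but not a rate.

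**8. Precision of a restricted rate.** The maximum 95% width is 19.9 points at n = 104 and 20.03 at n = 103, so the 20-point limit holds with up to six subjects excluded. It is 20.4, 21.7 and 23.2 points at n = 99, 88 and 77.

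**The case against.** The strongest reply is that most of the information is already planned. Each forest plot prints subjects, responses and the rate with its interval. If the lesion count is extracranial, adding the 1–2 and ≥3 rows gives a rate among treated subjects with extracranial target lesions, including those never rescanned. SAP 7.3.2 tabulates baseline extracranial target and non-target lesions. This reduces the gap but does not close it: the compartment must be guessed, non-target-only disease is left out, and the reader has to build the estimate.

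A second reply is that the answer may lie in text not supplied: Appendix 3, the Imaging Review Charter, redacted efficacy text, or the Data Presentation Plan that SAP 9 says holds the full list of analyses. That is a fair limit on the statement that no pooled rate is planned. It does not alter the denominator that Protocol 8.4.2 and SAP 4.2 state openly.

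Third, BOR is taken from the CRF, so a brain-only subject could in principle be entered as an extracranial CR. That would be a coding error, since a response needs a baseline lesion, and it is a further reason to state the rule.

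Finally, the all-treated rate is prespecified and consistent across both documents, and any added rate is post hoc in an open-label trial. These points stand, and they are why the prespecified rate should be kept and the new one labelled. The size is also hypothetical, since q is unknown.

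**Conclusion.** The concern holds. As written, extracranial ORR is the rate among subjects with extracranial disease scaled down by the share who have none, and extracranial CBR shifts in a direction that depends on an unstated coding rule. On an assumed 60% rate, the loss in ORR is 3 points at q = 5%, 12 at 20% and 18 at 30%; CBR could lie anywhere from 48% to 68% at q = 20%. If q proves very small, the matter is minor.

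The conclusion rests on the stated denominators, on eligibility that does not require extracranial disease, and on the premise that a response needs a baseline lesion. It does not touch the primary endpoint or OS, no hypothesis test depends on it, and nothing is claimed about the global rates. It should be fixed because two named secondary estimates cannot otherwise be read as their names suggest.

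**What to change.** In SAP 7.5.2.1 and 7.5.2.2:

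- Add investigator-assessed extracranial ORR and CBR among all treated subjects with any extracranial lesion, target or non-target, at baseline. Use this one denominator for both, and count subjects with no post-baseline assessment as non-responders and as no benefit.
- Keep the all-treated rates unchanged. Print beside them the number of subjects with no extracranial lesion, and state how their extracranial BOR is coded.
- State that the target-lesion count in each forest plot refers to that plot's compartment.
- Label the added rates as specified after the interim lock. SAP 4.1 says of its choice of primary BOR set, "This decision was made after the interim database lock on 09 August 2020", so the current SAP text already postdates that lock.

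The cost is SAP wording and one extra rate per endpoint. Baseline lesion data are already collected and summarised, and the protocol definition stays, so no protocol revision is needed. There are two drawbacks. The added ORR can only equal or exceed the all-treated one, so the post hoc label matters. Its interval will also be wider, passing the plan's 20-point limit once more than six subjects are excluded from 110.

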5 SAMPLE SIZE AND POWER

The total sample size for the treatment of nivolumab combined with ipilimumab is 110 subjects. All patients will contribute to the primary efficacy assessment. Cohort A will enroll asymptomatic subjects (n ~ 90), and Cohort B will enroll symptomatic subjects (n ~ 20).

Table 5-1: CA209204: Clinical Benefit Rates – two sided 90% confidence interval (Clopper-Pearson)

	Nivolumab+Ipilimumab (n=110)			
	Clinically meaningful CBR	Observed CBR	Clopper-Pearson exact two-side 90% CI	Clopper-Pearson exact two side 95% CI
Brain (intracranial)	40%	53/110 (48.2%)	(40.0%, 56.4%)	(38.5%, 57.9%)
Systemic (extracranial)/ Global (intracranial +extracranial)	50%	65/110 (59.1%)	(50.8%, 67.0%)	(49.3%, 68.4%)

Table 5-1 presents the CBRs that would have to be observed to yield clinically meaningful results with respect to the lower bounds of the Clopper-Pearson exact two sided 90% and 95% confidence interval (CI). The planned sample size ensures that the maximum width of the exact 90% CI for

any given CBR estimate does not exceed 18% and the maximum width of the exact 95% CI for any given CBR estimate does not exceed 20%.

If the observed intracranial CBR rate is 51.8%, the sample size of 110 will achieve 80.4% power to detect a difference of 11.8% (51.8% versus 40% historical intracranial CBR rate) with a type I error rate of 0.10 for the two-sided binomial test.

